#### i. **Biomarkers**

12mL of blood and 50mL of urine will be collected.

- a) Cell Adhesion Molecules (CAM)S
- b) Soluble vascular cell adhesion molecules sVCAM
- c) Soluble intercellular adhesion molecules sICAM
- d) s-e Selectin
- e) Oxidized Low density lipoprotein
- f) Myeloperoxidase.
- g) MicroRNA signatures for arterial, renal and retinal complications
- h) Telomerase
- i) DNA methylation/acetylation
- j) Glycomark
- k) Isoprostanes and proteomics
- l) Clotting profile

Log books will be returned

A subset of participants will be take part in a semi-structured interview within 4 weeks of completing the study.

# 8 Study devices

The following devices will be used in the study: User guides are included in appendix 15.10

- 1. Minimed Medtronic 670G
- 2. CONTOUR LINK glucometer
- 3. 4th generation glucose sensors, and sensor inserter
- 4. GST3C CGM transmitter

# Trial management

The day to day management of the study will be the responsibility of the Investigator at each centre. The Chief Investigator and Study Project Manager (PM) will maintain regular email correspondence with all investigators and study coordinators. The Chief Investigator, with the principal investigators will assume responsibility for the progress of the study in accordance with agreed timelines and milestones with the study funders. An independent Data Safety and Monitoring Board have also been established. The Study PM will liaise with the study teams in all centres to establish procedures and ensure that the study is carried out according to the protocol and to standards of GCP, with robust systems for reporting adverse events. The Data Manager will be responsible for the central preparations of data for presentation to the DSMB as requested.

Trial agreements have been established between all of the collaborating centres as well as with Medtronic for the provision of devices.

# 10 Data management

The Data Manager will be responsible for the central preparations of data for presentation to the DSMB as requested. At consent each subject will be given a unique identifying number based on their centre which will be used for data input to the centralized database. Study databases are developed "in house" and incorporate QC checks to ensure accurate data entry. Randomizations will be undertaken by the Investigators (or delegated person) in each centre. Pump information will be reviewed at each centre when uploaded by the participant, copied and de-identified. This deidentified copy with the participant's unique identifier code will be sent to the data manager in Perth.

# 11 Adverse Events and Safety Reporting

Each investigator has the responsibility to ensure arrangements are in place to record, notify, assess, report, analyse and manage adverse events in this study in order to comply with the Therapeutic Goods Administration (TGA) regulations and local Ethics requirements.

In addition, the following people at the lead site in Perth should be notified of all Serious Adverse Events immediately or within 24 hours of being made aware of the event to ensure appropriate notification to the DSMB.

[name]
Department of Endocrinology & Diabetes,
Princess Margaret Hospital for Children,
[name]
[contact];
[contact]

Associate [name]
Department of Endocrinology & Diabetes,
Princess Margaret Hospital for Children
[name]
[contact]
[contact]

#### **Definitions:**

**Adverse Event** Any undesirable clinical occurrence in a subject whether it is considered to be device related or not, that includes a clinical sign, symptom or condition and/or an observation of an unintended technical performance or performance outcome of the device.

#### **Adverse Device Event**

A clinical sign, symptom or condition that is causally related to the device implantation procedure, the presence of the device, or the performance of the device system.

#### **Serious Adverse Event**

A serious adverse event is to be reported within 24 hrs of notification that:

- Results in death
- Is life threatening
- Any in-patient hospitalisation or results in prolongation of existing hospitalisation
- Results in persistent or significant disability/incapacity
- Congenital anomaly/birth defect

HCL outpatient Version Number:6.0 Version Date:15/07/2019 All serious adverse events (SAEs) should be reported immediately to the sponsor except for those SAEs that the protocol or other document (e.g., Investigator's Brochure) identifies as not needing immediate reporting. The immediate reports should be followed promptly by detailed, written reports. The immediate and follow-up reports should identify subjects by unique code numbers assigned to the trial subjects rather than by the subjects' names, personal identification numbers, and/or addresses. The investigator should also comply with the applicable regulatory requirement(s) related to the reporting of unexpected serious adverse drug reactions to the regulatory authority (ies) and the IRB/IEC.

Adverse events and/or laboratory abnormalities identified in the protocol as critical to safety evaluations should be reported to the sponsor according to the reporting requirements and within the time periods specified by the sponsor in the protocol.

For reported deaths, the investigator should supply the sponsor and the IRB/IEC with any additional requested information (e.g., autopsy reports and terminal medical reports).

The investigator must inform the HREC and the TGA (where appropriate) of all serious or unexpected adverse events that occur during the trial and may affect the conduct of the trial or the safety of the participants or their willingness to continue participation in the trial; to inform the HREC as soon as possible of any new information from other published or unpublished studies which may have an impact on the continued ethical acceptability of the trial or which may indicate the need for amendments to the trial protocol.

The TGA require that all serious and unexpected adverse device events are reported to the Devices Clinical Section, Office of Blood, Devices and Tissues of the TGA in an expedited fashion (i.e. within 15 calendar days of first knowledge), or for fatal or life-threatening events, an initial or full report within 7 calendar days and a follow-up report if necessary within the 15 calendar day timeframe. All other adverse device reactions and adverse events are tabulated as per usual trial protocols and produced on request.

#### 11.1 Ethical considerations Informed Consent

All eligible subjects identified for the intervention study who wish to participate, will be asked to sign a consent form agreeing to the trial. The subjects recruited to the study who are under the age of consent will be able to provide informed consent and this will be obtained from their parents according to current ICH, Good Clinical Practice (GCP) and The National Statement on Ethical Conduct in Human Research 2007 (Updated May 2013). Children will not be able to give their legal consent but they will be asked to give assent and this will be appropriately documented. Both children and the parents will be provided with full information about the trial and adequate time to consider the risk/benefits of participation in the study. Subjects whose first language is not English will be provided with translated versions of information sheets and with interpreters to aid discussion before consent.

Consent will initially be obtained by the research nurse, who is not directly involved in routine clinical care of the participant and their families, to avoid any undue pressure to agree to participation. Written signed informed consent will be retained in the study site files. On achieving age of consent, the participants will be asked to sign forms agreeing to their continued involvement in the study. All participants will freely give their informed consent to participate in the study. A participant may decide to withdraw from the study at any time without prejudice to their future care.

HCL outpatient Version Number:6.0 Version Date:15/07/2019

Consent for health care professionals involved in the study to be surveyed during the trial using the mobile app will be implied by the willingness to complete the survey. A consent statement will be displayed before the user can proceed to the questions.

#### 11.2 No fault liability

All of the investigators and research personnel will be indemnified for negligent harm based on local health service provision and personal investigators medical insurance provision.

#### 11.3 Ethical committee review

The study protocol is to be seen and approved by the appropriate ethical review committees at all centres. Copies of the letters of approval will be filed in the study file.

#### 11.4 National Statement/Declaration of Helsinki & ICH Good Clinical **Practice**

The study is to be carried out in conformation with the spirit and the letter of the Declaration of Helsinki, and in accord with the National Statement on Ethical Conduct in Human Research (2007) and ICH Good Clinical Practice Guidelines.

#### 11.5 Sources of research material and confidentiality protections

All subjects will be allocated a unique Study Identification number and this will be used for the transfer of all data. Confidential data will be retained at the study sites in a secure study file. At all times the confidentiality of the subjects will be maintained, and reports to meetings and publications will not include confidential or data identifying individuals.

#### 11.6 **Changes to protocol**

Any proposed protocol changes will be submitted for Ethics Committee approval or notification. Any protocol change should be documented as a Protocol Amendment.

#### 11.7 Subject withdrawal

A subject may terminate participation in the study at any time without necessarily giving a reason and without any personal disadvantage. An investigator can stop the participation of a subject after consideration of the benefit/risk ratio. Possible reasons are:

- 1. Serious adverse events
- 2. Non-compliance
- 3. Technical grounds (e.g. participant moves away)
- 4. Early termination of the study at the request of the steering committee or DSMB.

# 12 Ownership of data and publication agreements

Ownership of data and publication protocols are outlines in the Clinical Trial Funding Deed.

## 15.1 Diabetes Distress Scales

PAID-Teen (12 – 16 years)

Which of the following diabetes issues are **currently** a problem for you? Place an X in one box on each line which gives the best answer for you.

		Not a problem	Minor problem	Moderat problen	Somewhat serious problem	Serious problem
1.	Feeling sad when I think about having and living with diabetes?					
2.	Not knowing if the mood or feelings I am having are related to my blood sugar levels.					
3.	Feeling overwhelmed by my diabetes regimen?					
4.	Feeling angry when I think about having and living with diabetes?					
5.	Feeling constantly concerned about food and eating					
6.	Worrying about the future and the possibility of serious complications?					
7.	Feeling upset when my diabetes management is "off track"					
8.	Feeling "burned-out" by the constant effort to manage diabetes					
9.	Feeling that I am not checking my blood sugars often enough					
10.	Feeling unclear about exactly what or how much I should be doing to take care of my diabetes properly					
11.	Not feeling motivated to keep up with my daily diabetes tasks					
12.	Feeling discouraged or defeated when I see high blood sugar results on my meter					
13.	Feeling that my friends or family act like "diabetes police" (e.g. nag about eating properly, checking blood sugars, not trying hard enough)					
14.	Feeling like my parents don't trust me to care for my diabetes					
15.	Feeling like I must be perfect in my diabetes management					
16.	Missing or skipping blood sugar checks					
17.	Feeling that my blood sugars are often swinging wildly, no matter how hard I try					
18.	Feeling that I am often failing with my diabetes					

HCL outpatient Version Number:6.0 Version Date:15/07/2019

Protocol	l Number:	Version	60	15/07/2	2019

	regimen			
19.	Feeling that my parents blame me for blood sugar numbers they don't like.			
20.	Feeling that my friends or family don't understand how difficult living with diabetes can be			
21.	Feeling that I can't control my eating			
22.	Feeling like my parents worry about complications too much			
23.	Worrying about my weight			
24.	Worrying that diabetes gets in the way of having fun and being with my friends			
25	Fitting my diabetes regimen into my day when I'm away from home (e.g. school, work, etc.)			
26	Worrying about getting low during a sports activity			
27.	Feeling like my parents worry about complications too much			

Problem Areas in Diabetes (PAID) © Joslin Diabetes Center 1999

PAID (16 years and older)

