### 3. Psychosocial:

Questionnaires will be conducted on 3 occasions: at baseline, 13 weeks and 26 weeks.

- **Fear of hypoglycaemia**: Hypoglycaemic Fear Survey-II Worry scale: 17-<25years. Children's Hypoglycaemia Fear survey 12 – 17 years.
- **Hypoglycaemia Awareness**: Hypoglycaemia Awareness Scale (Gold Score) (all ages) ii.
- **Anxiety**: State-Trait Anxiety Inventory (Child version for 12-15yrs, adult version ≥16iii. <25yrs)
- **Impact and Satisfaction**: The Diabetes Treatment Satisfaction Questionnaire status iv. and change version (16 - <25 years)
- Quality of Life: 12-<25 years: EQ-5D-Y, v.
- **Diabetes specific quality of life**: PedsQL –Child version (12 year olds), Adolescent vi. version (13-18) and young adult version (18-<25).
- **Diabetes distress:** Problem Areas in Diabetes (Teen version for 12 17 years, standard vii.  $version \ge 17 - <25 vr$
- Participant reported outcome for Automated Delivery system: INSPIRE viii. Questionnaires: baseline and post-assessment versions Child version (12 year olds), Adolescent version (13-18) and adult version(18-25)
- **Semi structure interview** (all ages post study, PCH only) ix.

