## 3. Psychosocial:

Assess the average difference between standard therapy (MDI and CSII) in the following measures:

- i. **Fear of hypoglycaemia**: Hypoglycaemic Fear Survey-II Worry scale: 17-<25years. Children's Hypoglycaemia Fear survey 12 17 years.
- ii. **Hypoglycaemia Awareness**: Hypoglycaemia Awareness Scale (Gold Score) (all ages)
- iii. **Anxiety**: State-Trait Anxiety Inventory (Child version for 12-15yrs, adult version ≥16-<25yrs)
- iv. **Impact and Satisfaction**: The Diabetes Treatment Satisfaction Questionnaire status and change version (16 <25 years)
- v. **Quality of Life**: 12-<25years: EQ-5D-Y,
- vi. **Diabetes specific quality of life**: PedsQL Child version (12 years) Adolescent version (13 18 years) and young adult version (18 <math><25 years).
- vii. **Diabetes distress:** Problem Areas in Diabetes (Teen version for 12 17 years, standard version  $\geq 17 \langle 25yr \rangle$
- viii. **Participant reported outcome for Automated Delivery system:** INSPIRE Questionnaires: baseline and post-assessment versions Child version (12 year olds), Adolescent version (13-18) and adult version(18-25)
- ix. **Semi structure interview** (all ages post study, PCH only)

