# Sensitivity analysis

The primary endpoint analysis will be re-run with the PP population as a sensitivity analysis. Secondary endpoints.

Coefficient of variation will be reported for each group: bootstrap methods will be used to estimate variability as appropriate.

Rates of hospitalisations for severe hypoglycaemia and moderate hypoglycaemia as per participant log will be analysed as unadjusted incidence rates based on the Poisson distribution. Incidence rates and incidence rate differences will be presented with their associated 95% confidence intervals calculated as exact Poisson confidence limits(22). In addition, where

HCL outpatient Version Number:6.0 Version Date:15/07/2019 appropriate Poisson or negative binomial regression models will be fitted e.g. moderate hypoglycaemia events from the participant log. If there are a high proportion of zero counts, zero inflated Poisson (ZIP) or zero inflated negative binomial models (ZINB) will be considered. If counts are sparse then rates will be reported descriptively only. Number of hospitalisations due to diabetic ketoacidosis events and other safety outcomes will be tabulated and presented as n and %.

Continuous outcome measures (including psychosocial) collected at baseline and endpoint will be analysed using ANCOVA adjusting for baseline score and site. Measures collected at baseline, 3 months and endpoint (e.g. *HbA1c*, *Fasting capillary blood glucose*, *Mean CGM glucose*, *Hypoglycaemic Fear Survey-II Worry scale*, *Child State-Trait Anxiety Inventory*, *The Diabetes Treatment Satisfaction Questionnaire status and change version*, *Problem Areas in Diabetes, Impaired awareness of hypoglycaemia: GOLD SCORE, INSPIRE questionnaires*) will be analysed using mixed models repeated measures (MMRM) adjusting for baseline score (where appropriate), group, period (baseline, 3 months, 6 months) and site. A random intercept term for 'individual' will also be employed if deemed appropriate. Least square means and least square mean differences and their associated 95% confidence intervals will be presented for each group and between groups. Unstructured covariance matrix will be used unless other covariance structures are more appropriate as determined by the Bayesian information criteria (BIC). Human technology interaction and health care professional experiences and expectations analyses will be reported Exploratory; descriptive analysis.

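### Lines 22 and 27 of the appended PAID-Teen form are identical, so the 27 printed lines hold 26 distinct items and one item counts double if every line is scored

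*Protocol*

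**What the plan says.** Appendix 15.1 of the protocol reproduces the diabetes distress questionnaires. The teen form has 27 numbered lines. Line 22 reads "Feeling like my parents worry about complications too much", and line 27 has the same words. The form for older participants, printed next in the same appendix, is a separate 20-item questionnaire with no repeated line.

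Section 6.3 lists diabetes distress among the secondary psychosocial endpoints and names the teen form as the instrument for the younger participants: "Problem Areas in Diabetes (Teen version for 12 17 years, standard version" for the older ones. Section 6.2.2 sets the timing: "Questionnaires will be conducted on 3 occasions: at baseline, 13 weeks and 26 weeks". Section 7.3 includes the instrument in its list of repeated measures, "Problem Areas in Diabetes, Impaired awareness of hypoglycaemia: GOLD SCORE, INSPIRE questionnaires", and says that these "will be analysed using mixed models repeated measures (MMRM) adjusting for baseline score (where appropriate), group, period (baseline, 3 months, 6 months) and site".

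The Visit 1 description in the visit schedule says that the psychological scales will be electronic where that applies. The protocol does not state how PAID-Teen is scored. It gives no item count, does not choose between a sum and a mean, and has no rule for the repeated line.

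**The concern.** A questionnaire score is meant to give each item its intended weight. When one question appears twice and all lines are added, that question counts double. Here it concerns the parents' worry about complications. A closed-loop system might change that differently from the participant's own distress, although the protocol offers no evidence on this. The score would then differ from that of a form that asks each question once, and its level would be harder to compare with PAID-Teen scores from other studies.

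Two further difficulties follow from the printed form. A participant can answer the two identical lines differently, and there is no rule for that case. The repeat may also be a sign that a different item was lost when the form was typed. In that event the form lacks a question as well as repeating one.

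**Working it through.** The protocol states no figure on this point, so there is none to reproduce. The check compares the printed lines and then works out the effect of the repeat.

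**Inputs from the protocol.** The teen form in Appendix 15.1 has 27 numbered lines. Lines 22 and 27 are identical word for word. Distinct items: 27 − 1 = 26.

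**Assumptions.** Each item is scored 0 to 4, and the total is rescaled to 0 to 100. The protocol gives neither.

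**Weight of the repeated item**
- Counted once: 1/26 = 0.0385, or 3.8%.
- All 27 lines scored: 2/27 = 0.0741, or 7.4%.

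**Shift for one participant.** Let x be the answer to the repeated item and m the mean of the 26 distinct items. The mean over 27 lines is (26m + x)/27, so it differs from m by (x − m)/27. On the 0 to 100 scale this is 25(x − m)/27.

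The largest upward shift occurs when x = 4 and all other answers are 0:
- 26 items: 4/104 = 3.85.
- 27 lines: 8/108 = 7.41.
- Shift: +3.56 points.

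The largest downward shift, with x = 0 and all other answers 4, is 100/108 − 100/104 = 92.59 − 96.15 = −3.56 points.

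Less extreme records, with the other 25 items all answered 1:

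| Answer to repeated item | 26 items, 0–100 | 27 lines, 0–100 | Shift |
|---|---|---|---|
| 4 | 29/104 = 27.9 | 33/108 = 30.6 | +2.7 |
| 2 | 27/104 = 26.0 | 29/108 = 26.9 | +0.9 |
| 1 | 26/104 = 25.0 | 27/108 = 25.0 | 0 |
| 0 | 25/104 = 24.0 | 25/108 = 23.1 | −0.9 |

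The rescaled score does not move when the repeated item equals the mean of the 26 items.

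**Effect on a difference between arms.** The same formula applies to mean differences. If the arm difference on the repeated item departs from the arm difference on the 26-item mean by one full item point, the score difference moves by 25/27 = 0.93 points out of 100. If the two are equal, it does not move.

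**Agreement of the two scorings.** In simulated records with 26 equally correlated normal items (inter-item correlation assumed), the correlation between the 26-item and 27-line scores was 0.9977, 0.9986, 0.9991 and 0.9994 for inter-item correlations of 0.2, 0.3, 0.4 and 0.5. The ranking of participants is almost unchanged.

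**The case against.** The strongest reply is that the protocol fixes no scoring rule. Instrument scoring is commonly left to the analysis plan or the instrument's manual, and either could count the repeated item once. A reader might infer from the form that every teen score counts the item double. The documents do not support that, because it holds only if all 27 lines are scored. This objection stands, and the double weight is stated here as conditional. It does not remove the defect, since a scoring rule cannot change what participants are asked.

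A reader might also infer that the distress comparison at 13 and 26 weeks rests on a distorted score. That goes too far. Participants on the standard form answer no repeated line, and both arms receive the same teen form at every visit. The repeat changes item weights; it does not by itself create a difference between arms.

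A third tempting inference is that line 27 is plainly surplus and the intended scale has 26 items. The documents do not show this. Line 27 may have displaced another question.

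Finally, the administered form may be an electronic one without the repeat, and the text at hand was read from a PDF that repeats text elsewhere. The first is possible and is a reason to check both versions. The second is unlikely here: line 27 has its own number, follows line 26 and stands directly before the copyright line.

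**Conclusion.** Wrong as written, minor. The duplicate is certain in the printed text, and it sits in the instrument for a stated secondary endpoint. If all lines are scored, the item's weight rises from 3.8% to 7.4%, and one participant's score shifts by at most about 3.6 points. That size rests on the assumed 0 to 4 scoring and 0 to 100 rescaling. The near-perfect agreement of the two scorings rests on the assumed item correlations. The effect is confined to participants given the teen form. Its main consequence is that the score is not that of a form with each item asked once, which weakens comparability with other PAID-Teen results.

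Appendix 15.1 and section 6.3 also give different age limits for the teen form (12 to 16 against 12 to 17). That is a separate matter, but it bears on how many participants meet the repeated line.

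**What to change.** Check the PAID-Teen form in Appendix 15.1, and the electronic version in use, against the licensed instrument. Then correct line 27 in both: delete it if it is surplus, or put back the right item if it displaced one. Deletion should not be prescribed before that check.

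For forms already completed with the repeat, state that the repeated item counts once, and name in advance which of the two answers is used when they differ (line 22, the first asked, would do). Use that score in the section 7.3 repeated-measures analysis.

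The cost is one form correction, one scoring sentence and a rescoring of completed forms, with no new data. If an item was displaced, the answers to it on earlier forms cannot be recovered, and the report should say so.
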